**a: Chi-square test; p< 0.05 is significant.**

**Table (3)** shows that 7.4% contacts developed diseases in ivermectin group while they were 58.4% in no-intervention group. Contacts tend to be infected when the index case was severe; 14.8% and 71.1% in both groups, respectively. The protection rate for ivermectin was more prominent in contacts less than 60 years old (6.2% infected compared to 58.7% if no intervention) , but still effective in elder than 60 years (16% infected compared to 55.6% if no intervention).

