## Consort Flow diagram of Ivermectin prophylaxis trial

## **Statistical analysis**

All data were collected, tabulated and statistically analyzed using SPSS 22.0 for windows (IBM Inc., Chicago, IL, USA) and MedCalc 13 for windows (MedCalc Software Bvba, Ostend, Belgium). Continuous Quantitative variables were expressed as the mean  $\pm$  SD & median (range), and categorical qualitative variables were expressed as absolute frequencies (number) & relative frequencies (percentage). Continuous data were checked for normality by using Shapiro Walk test. Mann-Whitney U test was used to compare between two groups of non-normally distributed data. Categorical data were compared using Chi-square test or Fisher's exact test when appropriate. Relative risk and its 95%Confidence interval (CI) was calculated to estimate risk of COVID-19 infection in addition forest plot was plotted. Univariate and multivariate binary logistic regression were built to find predictors for COVID-19 protection. All tests were two sided. p-value < 0.05 was considered statistically significant.

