**a: Chi-square test; b: Mann Whitney U test; p< 0.05 is significant.**

**Table (2)** shows that 15 contacts (7.4%) developed COVID-19 in the ivermectin arm compared to 59 (58.4%) in the no-intervention arm, all of them were symptomatic, according to the study protocol . The difference was highly significant ( $p<0.001$ ). The median (range) days for developing the disease was 2 (2-6) in ivermectin group compared and 4 (2-10) in the no-intervention group, the difference was significant ( $p<0.017$ ). Ten contacts (66.6%) developed symptoms in 1st 3 days in ivermectin group, and none developed it after 6 days. In the no-intervention arm, 25 (42.3%) developed symptoms in the 1st 3 days and continued to the 10 days.

HRCT of the chest was performed in 14 out 15 contacts and in 58 of the 59 contacts who developed symptoms in ivermectin and no-intervention groups, respectively. The missed one case in each arm had symptoms and positive RT-PCR without other investigations. Chest HRCT was positive for

COVID-19 in 7 (50%) and 28 (48.3%) in ivermectin and no-intervention groups, respectively.

Complete blood count was performed also in 14 and 58 contacts who developed symptoms in ivermectin and no-intervention groups respectively. Positive criteria in CBC was present in 12 (85.7%) and 53 (91.4%) in ivermectin and no-intervention groups respectively.

**Table (3): Comparison between Ivermectin arm and non-intervention arm regarding protection rate stratified by basic characteristics.**

|                     |          | Protection rate |                      | Testa  | p-value |
|---------------------|----------|-----------------|----------------------|--------|---------|
|                     |          | Ivermectin arm  | Non-intervention arm |        |         |
| All patients        |          | 92.6%           | 41.6%                | -----  | -----   |
| Index case severity | Mild     | 92.9%           | 35%                  | 11.381 | 0.001   |
|                     | Moderate | 95.6%           | 55.8%                | 42.666 | <0.001  |
|                     | Severe   | 85.2%           | 28.9%                | 29.928 | <0.001  |
| Age                 | ≤60      | 93.8%           | 41.3%                | 91.514 | <0.001  |
|                     | >60      | 84%             | 44.4%                | 5.320  | 0.034   |
| Gender              | Male     | 94.3%           | 42%                  | 53.482 | <0.001  |

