|                     | Female   | 90.7%           | 41.2%                | 42.278 | <0.001  |
| Any comorbidity     | No       | 95.5%           | 45.3%                | 77.474 | <0.001  |
|                     | Yes      | 83%             | 30.8%                | 19.899 | <0.001  |

|     |     |       |       |        |        |
|-----|-----|-------|-------|--------|--------|
| DM  | No  | 94.7% | 42.9% | 96.308 | <0.001 |
|     | Yes | 61.5% | 30%   | 2.253  | 0.214  |
| HTN | No  | 93%   | 44.3% | 81.372 | <0.001 |
|     | Yes | 87.5% | 23.1% | 12.272 | <0.001 |

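### The Results text says protection was greater under 60, but no test compares the age groups; a difference by age is not shown, and the over-60 estimate is imprecise

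*Combined protocol and SAP*

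**What the plan says.** The Statistical analysis section offers two tests for proportions: "Categorical data were compared using Chi-square test or Fisher's exact test when appropriate". It sets one threshold for everything: "All tests were two sided. p-value < 0.05 was considered statistically significant". It describes no interaction test, no subgroup plan and no handling of multiplicity. The protocol sections on aim, objectives and follow-up name no age subgroup and no cut at 60.

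Table (3) splits the protection rate by six characteristics. For age, the row for 60 or under reads "93.8% | 41.3% | 91.514 | <0.001" and the row for over 60 reads "84% | 44.4% | 5.320 | 0.034" (ivermectin rate, non-intervention rate, test statistic, p-value). No denominators are shown.

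The text below the table draws two conclusions. The first is "The protection rate for ivermectin was more prominent in contacts less than 60 years old (6.2% infected compared to 58.7% if no intervention"). The second is "but still effective in elder than 60 years (16% infected compared to 55.6% if no intervention"). The logistic models in Table (4) list arm and age as separate predictors and show no term for their interaction.

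**The concern.** Each clause gives the illness rate in both arms, so each is a statement about treatment effect. The first says that the effect is larger in younger contacts. That is a claim of effect modification, and it needs the two effects to be compared with each other. Two within-group p-values of different size do not do this: the younger group has 270 contacts and the older 34, so the p-values would differ widely even if the effect were the same.

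The second clause uses percentages that hide how few people stand behind them. A reader who sees 16% against 55.6% cannot tell that the comparison has nine untreated contacts.

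At stake is how readers apply the result by age: they may take away a graded benefit that was never tested, and a precision in older contacts that the data do not have. The overall comparison is not at stake.

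**Working it through.** **Inputs.** Arm sizes are 203 and 101 (Table 2). Events come from the text under Table (2): "15 contacts (7.4%) developed COVID-19 in the ivermectin arm compared to 59 (58.4%) in the no-intervention arm". Age-group rates, test statistics and p-values come from Table (3).

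**1. Rebuild the counts.** I tried every whole-number split of 15/203 and 59/101 by age against the printed rates. One split fits in each arm.

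| Age | Ivermectin ill/N | Non-intervention ill/N |
|---|---|---|
| 60 or under | 11/178 (6.2%) | 54/92 (58.7%) |
| Over 60 | 4/25 (16.0%) | 5/9 (55.6%) |

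**2. Reproduce the plan's figures.** Pearson chi-square from these counts is 91.514 and 5.320, both as printed. Over 60, the Pearson p is 0.021 and Fisher's exact p is 0.0343. The printed 0.034 is therefore Fisher's p beside a Pearson statistic, although the table footnote names only chi-square.

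**3. Effect within each age group.** RR is the ratio of illness risks, with SE(log RR) = √(1/a − 1/n₁ + 1/c − 1/n₀), where a and c are the ill in the ivermectin and non-intervention arms and n₁ and n₀ the arm sizes.

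- 60 or under: RR = (11/178)/(54/92) = 0.105; SE 0.305; 95% CI 0.058 to 0.191. OR 0.046 (0.022 to 0.097). Risk difference 52.5 points (41.9 to 63.2).
- Over 60: RR = (4/25)/(5/9) = 0.288; SE 0.547; 95% CI 0.099 to 0.841. OR 0.152 (0.028 to 0.830). Risk difference 39.6 points (4.1 to 75.1).

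**4. Compare the effects.** On the RR scale, the difference in log RR is −1.245 − (−2.251) = 1.006. Its SE is √(0.305² + 0.547²) = 0.626, so z = 1.61. The other scales follow the same way.

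| Scale (over 60 v 60 or under) | Estimate | 95% CI | p |
|---|---|---|---|
| Ratio of RRs | 2.74 | 0.80 to 9.33 | 0.11 |
| Ratio of ORs | 3.29 | 0.52 to 20.9 | 0.21 |
| Difference in risk differences | −13.0 points | −50.0 to +24.1 | 0.49 |

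The logistic likelihood-ratio test (p=0.22) and the Breslow-Day test (p=0.20) agree with the OR row.

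**5. Fragility over 60.** With one fewer untreated case (4/25 v 4/9), Fisher's p is 0.16. With one more treated case (5/25 v 5/9), it is 0.085.

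**6. Number of tests.** Table (3) has 3 + 2 + 2 + 2 + 2 + 2 = 13 subgroup rows. The over-60 p is the second largest; only the diabetes row, "61.5% | 30% | 2.253 | 0.214", is larger. Adjusted over 13 tests, 0.034 becomes:

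- Bonferroni: 13 × 0.034 = 0.44
- Holm or Hochberg: 2 × 0.034 = 0.068
- Benjamini-Hochberg: 0.034 × 13/12 = 0.037

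**7. Clustering.** Contacts share index cases, and no described analysis allows for this. The documents give no intraclass correlation. As an assumption only, dividing 5.320 by a design effect of 1.2, 1.5 or 2.0 moves the Pearson p from 0.021 to 0.035, 0.060 or 0.10.

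**The case against.** **The sentence may be only descriptive.** It does not claim significance, and on all three scales the point estimates do favour younger contacts. That is true as far as it goes. But a Results statement that an effect is larger in one group, with both arms' rates attached, will be read as a finding, and nothing tells the reader that the difference was not tested.

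**A reader might infer that the over-60 claim is wrong.** The documents do not support that. The RR of 0.288 has an interval that excludes 1. It points the same way as the overall RR, (15/203)/(59/101) = 0.126. If the effects do not clearly differ by age, the older group may fairly borrow support from the whole: the age-stratified Mantel-Haenszel OR is 0.055 (0.028 to 0.108). This objection stands. The fault in the second clause is missing imprecision, not a wrong direction.

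**A reader might infer that multiplicity overturns p=0.034.** That depends on the method: it fails Bonferroni, Holm and Hochberg and passes Benjamini-Hochberg. Twelve of the 13 rows are below 0.05, and 11 of them are at 0.001 or below, so this row is not a lone positive among nulls. Small numbers and fragility are the firmer grounds.

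**A reader might infer that the effect is the same at all ages.** That is not supported either. If the true ratio of RRs were 2.74, the chance of detecting it with these standard errors would be about 36%; for a true ratio of ORs of 3.29 it would be about 24%. A non-significant interaction here says little.

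**Clustering.** Without household sizes by arm or an intraclass correlation, one can say only that the intervals may be too narrow.

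**Conclusion.** The concern holds for the first clause and, in a limited form, for the second. A larger effect under 60 is untested and not established: the ratio of RRs is 2.74 with an interval from 0.80 to 9.33. It is not ruled out. Benefit over 60 agrees in direction with the overall result, but it rests on 4/25 v 5/9, on an interval running from about a 90% to a 16% reduction in risk, and on an unadjusted p-value that one changed outcome would move above 0.05.

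This rests on counts that are derived, not printed, though they are the only ones that fit and they return both printed chi-squares. It also treats contacts as independent. It matters for one stated conclusion and leaves the headline comparison untouched.

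**What to change.** - In Table (3), print ill/N by arm for the two age groups, with the effect estimate and its 95% CI.
- Report one arm-by-age interaction test, using the recorded age in years and not the cut at 60.
- Reword the text under Table (3) to say that a difference in effect by age is not shown, and that the over-60 estimate is in the same direction as the overall result but imprecise (4/25 v 5/9).
- Label the Table (3) subgroup p-values as unadjusted and exploratory, and note that the intervals do not allow for shared households.

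The cost is one model term, a few table cells and a rewritten sentence; no new data are needed. The downside for the authors is a weaker statement about age.

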**Table (4): Predictors for COVID-19 protection.**

|                            | Univariate Model      |         | Multivariate Model    |         |
|----------------------------|-----------------------|---------|-----------------------|---------|
|                            | OR (95%CI)            | p-value | OR (95%CI)            | p-value |
| Arm                 |                       |         |                       |         |
| Ivermectin                 | 12.533 (7.408-21.205) | <0.001  | 11.445 (4.444-29.475) | <0.001  |
| Non-intervention           | Reference             |         |                       |         |
| Index case severity |                       |         |                       |         |
| Mild                       | 1.429 (0.722-2.828)   | 0.306   | 1.257 (0.486-3.247)   | 0.637   |
| Moderate                   | 6.120 (4.010-9.341)   | <0.001  | 2.816 (1.355-5.851)   | 0.006   |

| Severe          | Reference           |        |                     |       |
|-----------------|---------------------|--------|---------------------|-------|
| <hr/>           |                     |        |                     |       |
| Age             |                     |        |                     |       |
| Age≤60 years    | 3.154 (2.386-4.169) | <0.001 | 0.254 (0.101-0.639) | 0.004 |
| Age>60 years    | Reference           |        |                     |       |
| <hr/>           |                     |        |                     |       |
| Gender          |                     |        |                     |       |
| Male            | 3.457 (2.373-5.036) | <0.001 | 0.836 (0.437-1.600) | 0.588 |
| Female          | Reference           |        |                     |       |
| <hr/>           |                     |        |                     |       |
| Any comorbidity |                     |        |                     |       |
| Absent          | 3.812 (2.774-5.239) | <0.001 | 2.222 (0.967-5.108) | 0.060 |
| Present         | Reference           |        |                     |       |

**OR: Odds Ratio; 95%CI: 95%Confidence Interval.**

**Table (5)** shows that ivermectin have very highly significant role in the protection of SARS-CoV-2 infection. . It has an OR of 12.533 and 11.445 when compared to no intervention in both univariate and multivariate models, respectively. Ivermectin protection was not affected by gender or comorbidities in multivariate model.

As regard ivermectin side effects, they were reported in 11 (5.4%) contacts. These were; diarrhea (1.5%), nausea (1%), fatigue (1%), sleepiness (0.5%), abdominal pain (0.5%), heart burn (0.5%), tingling and numbness (0.5%) and lastly burning sensation (0.5%)

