| Protection      | 188 | 92.6% | 42 | 41.6% | a       |        |

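### The univariate odds ratios in Table (4) are odds within a single category, not ratios against the reference; the crude ivermectin OR is 17.6, not 12.533

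*Combined protocol and SAP*

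**What the plan says.** The Statistical analysis section names univariate and multivariate binary logistic regression for predictors of protection, with two-sided tests at 0.05. Table (4) labels its entries as odds ratios with 95% CIs. Each has a named reference: non-intervention, severe index case, age over 60, female, or comorbidity present.

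The univariate rows include ivermectin "12.533 (7.408-21.205"), age up to 60 "3.154 (2.386-4.169") and male "3.457 (2.373-5.036"), all with p<0.001. The multivariate column gives "11.445 (4.444-29.475") for ivermectin and "0.254 (0.101-0.639") for age up to 60.

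The text below the table, which calls it Table (5), reads: "It has an OR of 12.533 and 11.445 when compared to no intervention in both univariate and multivariate models, respectively". It adds: "Ivermectin protection was not affected by gender or comorbidities in multivariate model". The protection row of Table (2) reads "188 | 92.6% | 42 | 41.6"%, for ivermectin and non-intervention respectively.

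**The concern.** An odds ratio against no intervention must use the counts of both arms. The printed 12.533 can be obtained from the ivermectin arm alone. If the whole column was built this way, each p-value tests whether the odds of protection in one category differ from 1 (that is, whether protection differs from 50%), not whether the category differs from its reference. Because about three quarters of all contacts were protected (230 of 304), almost any large category would then look like a highly significant predictor.

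At stake are the effect size quoted in the text, the apparent predictive value of age and sex, and trust in the multivariate column of the same table.

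**Working it through.** **Inputs.** Arm counts come from Table (2): 188 protected and 15 not on ivermectin, 42 and 59 without intervention. Counts for the other rows were rebuilt from the percentages and chi-squares in Table (3) with the arm totals 203 and 101. Each stratum has only one integer solution. Protected/not protected, ivermectin then non-intervention:

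- Mild 13/1 and 7/13; moderate 129/6 and 24/19; severe 46/8 and 11/27.
- Age up to 60: 167/11 and 38/54; over 60: 21/4 and 4/5.
- Male 100/6 and 21/29; female 88/9 and 21/30.
- No comorbidity 149/7 and 34/41; comorbidity 39/8 and 8/18.

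All 13 chi-squares in Table (3) reproduce from the rebuilt counts (for example 11.381, 42.666, 29.928 and 91.514). Gender and comorbidity totals match Table (1).

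**Step 1: reproduce the printed figures.** With a protected and b not protected in one category, odds = a/b and 95% CI = exp[ln(a/b) ± 1.96·√(1/a + 1/b)]. For ivermectin, 188/15 = 12.533. The standard error is √(1/188 + 1/15) = 0.268, giving 7.408 to 21.205, exactly as printed. The other five rows also match in estimate and limits, and the mild row returns its printed p=0.306. A logistic model with no intercept produces exactly these values.

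**Step 2: compute the stated quantity.** OR = (a/b)/(c/d), with c and d from the reference category and 95% CI = exp[ln OR ± 1.96·√(1/a + 1/b + 1/c + 1/d)]. For the arm, (188/15)/(42/59) = 12.533/0.712 = 17.6.

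| Row | Category odds (= printed OR) | Reference odds | OR against reference (95% CI) | p, printed | p, recomputed |
|---|---|---|---|---|---|
| Ivermectin | 188/15 = 12.533 | 42/59 = 0.712 | 17.6 (9.1–34.0) | <0.001 | <0.001 |
| Mild | 20/14 = 1.429 | 57/35 = 1.629 | 0.88 (0.39–1.96) | 0.306 | 0.75 |
| Moderate | 153/25 = 6.120 | 57/35 = 1.629 | 3.76 (2.07–6.82) | <0.001 | <0.001 |
| Age ≤60 | 205/65 = 3.154 | 25/9 = 2.778 | 1.14 (0.50–2.56) | <0.001 | 0.76 |
| Male | 121/35 = 3.457 | 109/39 = 2.795 | 1.24 (0.73–2.09) | <0.001 | 0.43 |
| No comorbidity | 183/48 = 3.812 | 47/26 = 1.808 | 2.11 (1.19–3.75) | <0.001 | 0.011 |

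From the same Table (2) counts, the relative risk of infection is (15/203)/(59/101) = 0.126 (0.076 to 0.212).

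**Step 3: the multivariate column.** Its age OR of 0.254 (p=0.004) sits oddly with crude protection of 205/270 = 75.9% up to 60 and 25/34 = 73.5% over 60. The joint covariate table is not published, so models were refitted 2,400 times on simulated data that keep every published margin. The share of those over 60 with a comorbidity was assumed between 30% and 100%, or left random.

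- Without intercept: arm OR 12.1–14.2 (SE 0.336–0.349), age OR 0.12–0.49.
- With intercept: arm OR 16.6–20.0 (SE 0.357–0.380), age OR 0.36–2.91.

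The printed age OR lies only in the no-intercept range. The printed arm OR of 11.445, with SE ln(29.475/4.444)/3.92 = 0.483, lies in neither. These are simulation ranges, not bounds.

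**Step 4: does protection vary by subgroup?** Arm ORs from the Table (3) counts:

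- Men 23.0, women 14.0: ratio 1.65 (0.43–6.25), p=0.46.
- Without any comorbidity 25.7, with 11.0: ratio 2.34 (0.56–9.81), p=0.25.
- Without diabetes 24.0, with 3.7: ratio 6.43 (0.95–43.5), p=0.056.
- Without hypertension 16.8, with 23.3: ratio 0.72 (0.09–5.81), p=0.76.

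**Step 5: clustering.** The 304 contacts fall under 9 + 44 + 23 = 76 index cases, a mean of 4.0 each. Assuming equal clusters and an intra-cluster correlation of 0.1 to 0.3 (not in the documents), the design effect 1 + 3·ICC is 1.3 to 1.9. The arm CI widens to 8.3–37.3 and 7.1–43.6 respectively.

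**The case against.** The central arithmetic is not open to dispute, and extraction from PDF cannot explain it. The case on the other side concerns reach.

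- **Consequence.** The error understates the crude arm OR, so the direction and significance of the arm effect do not change. The text never presents age or male sex as univariate predictors, and the multivariate gender row is already non-significant (p=0.588). The planned method is sound; the fault lies in execution of a secondary analysis. All of this stands, but an effect size quoted in the text and a full column are still wrong as labelled.
- **Multivariate column.** Only 12.533 is shown to be wrong; 11.445 is not. This also stands. A refit is warranted, and 11.445 should change to whatever the refit gives.
- **Interactions and clustering.** These are separate from the odds error and go beyond the analyses named in the Statistical analysis section. Diabetes is not a term in Table (4), and hypertension points the opposite way. That is fair, and both are shown above. The hypertension interval is itself very wide, which supports the point that these data cannot establish uniform protection. Even the widest clustered interval is far from 1. A change of wording is enough on both matters if no new analysis is wanted.

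**Conclusion.** The concern holds. All six univariate entries in Table (4) are one-category odds, and 12.533 is not the OR against no intervention; that OR is 17.6 (9.1 to 34.0). At the 0.05 level, age and gender lose significance. Arm, moderate severity and absence of comorbidity keep it. Mild severity stays non-significant but moves from above 1 to below 1.

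The arm row needs only Table (2). The other rows rest on the counts rebuilt from Table (3), which are unique and reproduce every chi-square there. All recomputed intervals treat contacts as independent.

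Confidence is high for the univariate column. It is only moderate that the multivariate model also lacks an intercept, since neither model tried reproduces its arm row. That column, including the apparent harm of younger age, should not be relied on until refitted. The statement that protection was unaffected by gender or comorbidities is not supported: main-effect terms do not address it, and the subgroup ratios are too imprecise to show it.

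**What to change.** 1. Refit all univariate and multivariate models in Table (4) on the individual data with an intercept. Replace both columns with the output.
2. Update both ORs in the sentence below the table from the refit, and correct its reference to Table (5).
3. State which terms and records the multivariate model contains.
4. For the sentence on gender and comorbidities, either report arm-by-covariate interaction terms with CIs or say only that no interaction was shown, if the refit bears that out.
5. Report the relative risk with its CI, already named in the Statistical analysis section, beside the ORs.
6. Either allow for clustering under index cases (for example GEE or cluster-robust standard errors) or state that the intervals ignore it.

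The cost is a rerun of existing models, one corrected table and two corrected sentences, with no new data. Interaction terms and cluster-adjusted errors would be modest additional analyses; the wording alternatives in items 4 and 6 avoid them.

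### The statement that gender and comorbidities did not affect ivermectin protection does not follow from Table (4), and the univariate OR beside it is not an odds ratio against no intervention

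*Combined protocol and SAP*

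**What the plan says.** The Statistical analysis section plans univariate and multivariate logistic regression to look for predictors of protection. It names no interaction or heterogeneity test.

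Table (3) compares the arms within each stratum and does not compare strata with one another.

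Table (4) lists arm, index-case severity, age, gender and any comorbidity, with no arm-by-factor row. Its multivariate column gives gender as "0.836 (0.437-1.600) | 0.588" and absence of comorbidity as "2.222 (0.967-5.108) | 0.060".

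The text below that table (which calls it Table (5)) says of ivermectin: "It has an OR of 12.533 and 11.445 when compared to no intervention in both univariate and multivariate models, respectively". It then concludes: "Ivermectin protection was not affected by gender or comorbidities in multivariate model".

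**The concern.** The natural reading of the concluding sentence is that ivermectin protected men and women, and people with and without comorbidity, to the same degree. That is a claim about interaction, and no reported analysis tested it. A non-significant main effect says nothing about whether the arm effect varies across levels of the factor. A reader could take the sentence as evidence of uniform benefit when the subgroup counts are too sparse to show it.

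The sentence could instead mean that the arm effect held up after adjustment. The text offers the pair 12.533 and 11.445 for that comparison, but the first figure is not an odds ratio between the arms, so the pair cannot be compared.

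**Working it through.** **1. The printed p-values are main-effect tests.** With SE = ln(upper/lower)/(2×1.96) and z = ln(OR)/SE from Table (4), multivariate column:

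- Gender: SE = ln(1.600/0.437)/3.92 = 0.331; z = ln(0.836)/0.331 = -0.54; p = 0.588, as printed.
- Comorbidity absent: SE = ln(5.108/0.967)/3.92 = 0.425; z = ln(2.222)/0.425 = 1.88; p = 0.060, as printed.

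**2. Subgroup counts.** Table (1) denominators and Table (3) percentages each fit a single whole number protected:

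| Stratum | Ivermectin | No intervention | Chi-square, recomputed and printed |
|---|---|---|---|
| Male | 100/106 | 21/50 | 53.482 |
| Female | 88/97 | 21/51 | 42.278 |
| Comorbidity absent | 149/156 | 34/75 | 77.474 |
| Comorbidity present | 39/47 | 8/26 | 19.899 |

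**3. Ratio of odds ratios.** The SE of its log is the square root of the sum of the reciprocals of all eight cells.

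- Gender: male (100×29)/(6×21) = 23.02; female (88×30)/(9×21) = 13.97; ratio 1.65; SE 0.680; 95% CI 0.43-6.25; p = 0.46.
- Comorbidity: absent (149×41)/(7×34) = 25.67; present (39×18)/(8×8) = 10.97; ratio 2.34; SE 0.731; 95% CI 0.56-9.81; p = 0.24.

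Likelihood-ratio interaction tests agree (p = 0.46 and 0.25). The intervals run from about a halving to a six- to tenfold ratio.

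**4. Other scales, for comorbidity.**

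- Infection relative risk: absent (7/156)/(41/75) = 0.082; present (8/47)/(18/26) = 0.246; ratio 0.33 (0.12-0.92), nominal p = 0.034.
- Risk differences: 95.5 - 45.3 = 50.2 points (absent) and 83.0 - 30.8 = 52.2 points (present), nearly equal.
- For gender, the ratio of relative risks is 0.62 (0.22-1.77), p = 0.37.

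**5. The univariate column.** Within-level odds are a/b with SE = √(1/a + 1/b). For the arm row, 188/15 = 12.533, SE = 0.268, 95% CI 7.41-21.21, which matches the printed "12.533 (7.408-21.205" to rounding. The remaining rows match in the same way:

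- mild 20/14 = 1.429
- moderate 153/25 = 6.120
- age 60 or under 205/65 = 3.154
- male 121/35 = 3.457
- no comorbidity 183/48 = 3.812

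(Severity and age counts are rebuilt from the Table (3) percentages.) A logistic model fitted without an intercept gives exactly this.

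The odds ratio against no intervention uses both arms of Table (2), whose protection row reads "188 | 92.6% | 42 | 41.6": (188×59)/(15×42) = 11092/630 = 17.6. Its SE is √(1/188 + 1/15 + 1/42 + 1/59) = 0.336, so the 95% CI is 9.1-34.0.

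**6. Adjustment for one factor at a time.** Mantel-Haenszel arm odds ratios are 17.5 (9.0-33.8) for gender and 18.9 (9.5-37.7) for comorbidity, against 17.6 crude.

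**7. Why the multivariate column also needs checking.** With an intercept and arm in the model, absence of comorbidity has OR 2.74 (1.31-5.70, p = 0.007), and age 60 or under has OR 1.68 (0.61-4.60). Table (4) prints 2.222 (p = 0.060) and, for age, "0.254 (0.101-0.639) | 0.004". The printed model has more covariates, so the differences do not prove an error. They are a reason to refit.

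**The case against.** **The sentence may only restate the predictor results.** It names exactly the two factors that were non-significant in the multivariate column, in a table about predictors. This is plausible, and it makes the point one of wording. But p = 0.060 with an interval of 0.967-5.108 does not show that comorbidity has no effect, and the sentence makes protection by ivermectin its subject.

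**The multivariate arm estimate supports persistence after adjustment.** On its face it does: 11.445 (4.444-29.475), with gender and comorbidity in the same model, and the one-factor estimates in step 6 point the same way. A reader might infer from the univariate error that the multivariate estimate is wrong too. The documents do not establish that, because the joint distribution of the covariates is not given and the model cannot be refitted from them.

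**A reader might infer that comorbidity does modify the effect, citing the relative-risk p of 0.034.** The documents do not support that either. The result is post hoc, unadjusted and specific to one scale. It misses a Bonferroni threshold even for two factors on two scales (0.05/4 = 0.0125). Moving one ivermectin-arm contact with comorbidity between outcomes changes p to 0.016 or 0.072. It appears to be driven by the 23 diabetic contacts: without them the relative risk with comorbidity is (3/34)/(11/16) = 0.128, and the comparison with those without comorbidity gives p = 0.52.

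**Interaction tests would be nearly uninformative.** This stands. At the SEs in step 3, 80% power needs a ratio of odds ratios of about exp(2.80×0.680) = 6.7 for gender and exp(2.80×0.731) = 7.8 for comorbidity. Omitting such tests is not itself an error; drawing a conclusion that needs them is.

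**Conclusion.** The concluding sentence is not supported as an absence of effect modification. On the odds-ratio scale, modification by gender (1.65, 0.43-6.25) or comorbidity (2.34, 0.56-9.81) is neither established nor excluded. The sentence before it is wrong on a figure: the univariate arm odds ratio against no intervention is 17.6 (9.1-34.0), not 12.533, and the whole univariate column consists of within-level odds.

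The ratios are unadjusted and treat contacts as independent, although contacts share index cases. The documents do not allow the effect of that clustering on these contrasts to be derived. If the variance were inflated by an assumed factor of 1.5 to 2, the intervals would widen to 0.32-8.43 up to 0.25-10.85 (gender) and 0.40-13.53 up to 0.31-17.75 (comorbidity), and the relative-risk p for comorbidity would become 0.08 to 0.13.

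Nothing here changes the main arm comparison in Table (2). The crude odds ratio is in fact larger than the figure printed.

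**What to change.** 1. Refit the Table (4) models with an intercept and replace the univariate column; the arm row becomes 17.6 (9.1-34.0). Confirm or correct the multivariate column in the same run.
2. Correct the univariate figure in the text below the table.
3. Replace the concluding sentence with, for example: *Gender and any comorbidity were not statistically significant predictors in the multivariate model* (only if the refit confirms this). *Modification of the ivermectin effect by gender or comorbidity was not tested and, on the odds-ratio scale, is neither established nor excluded.*
4. If persistence of the arm effect after adjustment is to be claimed, say so directly and give the refitted arm odds ratio with its interval.
5. Optionally, report arm-by-gender and arm-by-comorbidity terms with 95% CIs and standard errors clustered by index case, labelled exploratory, and adapt the words *was not tested* in item 3 accordingly.

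No new data are needed. The cost is a little re-analysis and a less definite subgroup statement. With only 15 events in the ivermectin arm, the optional terms will be imprecise.
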